HCP PLUS Peer Support Arm –employs a dual strategy where HCP support is provided as in the HCP Arm and a peer support component is added. The peer support is provided via participating in a peer support program that uses groups and 1:1 conversations to provide peer support. In this program COPD patients and family caregivers will be connected with ‘expert’ patients and caregivers also referred to as ‘peer mentors’/‘BREATHE Pals’. These mentors are COPD patients and caregivers who have successfully managed COPD and have received foundational training on peer mentoring. Peer mentors are nominated by their medical providers as successful COPD self-managers and all patient peer mentors have completed an acute pulmonary rehabilitation program and are current non-smokers thus serving as positive role models. Peer mentors are trained to listen and share their experiences with having COPD and overcoming its challenges, without provision of any medical advice. They are also trained about HIPPA and keeping all their conversations with program participants confidential. The peer support is provided using multiple channels including group and 1:1 conversations. All program participants will be invited to 8 group sessions over 6 months period. The sessions will be led by 1-2 peer mentors and discuss COPD self-management topics. At each of these sessions, a social worker would be present to support the peer mentors and facilitate any ‘difficult conversations’ that may arise. The group leaders will be trained to promote a friendly and non-hierarchical group environment. The program will encourage all participants to use group formats as often as possible to maximize benefits of peer and social support. Participants in the peer support program will also receive 1:1 peer support via having phone conversations with the peer mentors.

The peer mentors/Breathe Pals will have their own support structure to ensure continued participation, interest, and reciprocal benefits. Based on earlier studies we anticipate that the

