Peer support group conversations will be orchestrated at 8 'Get Together' events spanning a 6 months period. All participants who miss an event or were not interested/able to attend an event (based on preference, life circumstances, or health status), will be offered the option of attending a similarly themed 'BREATHE group call' to catch up on missed event conversations and their 'matched' BREATHE Pal will also contact him/her via phone to check in on them, answer any questions they have, and encourage them to attend the next Get together event. At end of these phone calls, the peer mentor has the option of talking about their call with the social worker. If a patient or a family caregiver expressed the need for additional healthcare or social support services, or if the peer mentor felt that they need it, they would inform the social worker who will facilitate the patient or family-caregiver access to these services.

At the group events (in person or group call), the group participants led by the BREATHE Pals will discuss COPD and its challenges, and share their experiences in coping with and managing it. See summary table below on general topics for discussion. The topics pertain to advancing patient understanding of COPD and its treatment options, introducing effective coping skills, and reinforcing a variety of positive behaviors including adherence to treatment plans, smoking cessation, joining pulmonary rehabilitation programs, and assuming an active, healthy lifestyle. The Breathe pals will use the COPD Patient Education guide and a set of commonly asked questions and answers (Commonly Asked Questions and Answers) as their content guide/reference for the group conversations and follow up phone conversations. Each meeting will include: 1) Education about COPD management strategies based on the themes in table below; 2) discussion of patient experiences and challenges related to using these strategies; and, 3) encouragement to set goals and problem solve challenges. The sessions will follow a sequence of themes from 1-8 and then repeat. A study participant may thus join the sessions sequence at any time point and continue for 8 sessions thus getting to participate in all 8 themes. If at any point the number of participants attending the sessions exceeded 20 people, the group will be split into two and new participants may join either group according to their preferred group meeting time.

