adherent participants all those patients who experienced at least four or more encounters with their peer mentor. We will also conduct sensitivity analyses in the same manner as for the primary outcome.

Intervention Implementation Analysis

In addition to assessing the primary and secondary outcomes for patients we intend to investigate which patient characteristics determine participation in the HCP PLUS Peer Support. That is, we will investigate which patient characteristics are related to attendance at BREATHE get togethers, participation in BREATHE calls, and phone interactions with BREATHE pals. As in the CACE analysis, we will define overall participation in the HCP PLUS Peer Support group as experiencing at least 4 or more encounters with a peer mentor either by attending a get-together, participating in a BREATHE call, or having a phone conversation. We will define participation in group support via attendance at 4 or more BREATHE get togethers or BREATHE calls. We will define participation in individualized 1:1 support by 4 or more encounters with a BREATHE pals over the phone. We will use multivariable logistic regression to predict overall participation, as well as participation in group or 1:1 support , from baseline characteristics such as age, gender, education level, distance from patient's home to meeting location, oxygen use, whether patient lives alone, whether patient reports they have a caregiver, self-reported health status, PAM level, and baseline assessments of hope, support, anxiety and depression from Herth Hope Index and PROMIS measures.

Heterogeneity of Treatment Effect (HTE) (PCORI Standard HT-1, HT-2, and HT-3)

HT-1, HT-3:

The goal of the HTE analyses in this study is to consider the difference in treatment effect between the two groups, taking into consideration differences in the groups that are not obviously accounted for in the balance created by the randomization scheme. Patient characteristics such as disease severity or caregivers' presence may show differences in the intervention's effect and thus are important avenues to explore for hypothesis generation. In these hypothesis generating HTE analyses, we will consider the following subgrouping variables for the primary outcome of change in SGRQ from baseline to 6 months: age (4 categories),

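### The implementation analysis reduces all three participation counts to 4 or more versus fewer and never models the counts, which probably costs power to find who participates

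*Combined protocol and SAP*

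**What the plan says.** The SAP states the aim of the Intervention Implementation Analysis as follows: "we will investigate which patient characteristics are related to attendance at BREATHE get togethers, participation in BREATHE calls, and phone interactions with BREATHE pals". It then defines three outcomes, each yes or no:

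- Overall participation: "at least 4 or more encounters with a peer mentor either by attending a get-together, participating in a BREATHE call, or having a phone conversation", with the cut taken expressly from the CACE analysis.
- Group participation: "We will define participation in group support via attendance at 4 or more BREATHE get togethers or BREATHE calls".
- 1:1 participation: "We will define participation in individualized 1:1 support by 4 or more encounters with a BREATHE pals over the phone".

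The model is the same for all three: "We will use multivariable logistic regression to predict overall participation, as well as participation in group or 1:1 support". The predictors are a list of baseline characteristics. No count or ordinal model is planned and no other cut is tried in this section. The definition with at least 2 encounters, in the CACE section, is a sensitivity analysis for the CACE only.

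Two other places matter. On the intervention, the protocol (section 4, Description of Study Arms) says: "All program participants will be invited to 8 group sessions over 6 months period". The SAP's Heterogeneity of Treatment Effect section takes the fitted probability of adherence from the implementation analysis and uses it to form low and high propensity subgroups.

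**The concern.** Group attendance has a natural scale from 0 to 8, and phone contacts are a count. Cutting both at 4 removes the contrast between never attending and attending a little, which is much of what an implementation analysis wants to know. It also removes the contrast between attending half the programme and all of it.

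The reason for the cut does not carry over. The SAP says that the CACE analysis requires patients to be divided into adherent and non-adherent; a regression on predictors of participation has no such requirement. In its Statistical Analysis section the SAP gives cumulative counts, such as hospital and ED visits, a Poisson or negative binomial model. That rule is written for secondary outcomes and does not formally cover participation, but it shows that the team models counts as counts elsewhere.

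At stake is the chance of detecting real predictors of participation, such as distance from the meeting place, oxygen use or living alone, in one arm of the trial.

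**Working it through.** **Inputs from the documents.** The SAP's Study Design section gives 290 patients randomised 1:1, so 290 / 2 = 145 in the peer support group. There are 8 sessions and the cut is 4. The protocol's figure of 145 per arm with 80% power (section 7c) concerns the SGRQ comparison. It gives no standard deviation, so it cannot be reproduced, and it says nothing about this analysis. No power, expected participation or predictor effect is stated for the implementation analysis, so there is no figure of the plan's own to reproduce.

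**Assumptions.** Two-sided alpha of 0.05, and the attendance patterns and effect sizes shown below.

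**Step 1: normal-theory benchmark.** If a normal outcome is cut so that a share p lies above the cut, the relative efficiency is E = φ(z)² / [p(1 − p)], where z is the normal quantile at p. If the uncut analysis has 80% power, the power after the cut is Φ(2.80 × √E − 1.96), with 2.80 = 1.96 + 0.84.

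| Share reaching 4 | E | Power after the cut | Loss (points) |
|---|---|---|---|
| 50% | 0.637 | 61% | 19 |
| 40% | 0.622 | 60% | 20 |
| 30% | 0.576 | 57% | 23 |
| 20% | 0.490 | 50% | 30 |
| 10% | 0.342 | 37% | 43 |

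For p = 0.5: 2.80 × √0.637 = 2.24, and Φ(2.24 − 1.96) = 0.61. With 95% reference power and an even split, the loss is 13 points.

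**Step 2: smooth variation in sessions out of 8.** Beta-binomial attendance, n = 145, mean attendance 30-60%, within-patient correlation 0.2-0.6, log odds 0.3 per SD of one predictor.

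- A rank test on the 0-8 count gains about 10-20 points over logistic regression at 4 or more. At mean 45% and correlation 0.4, power was 52% with the cut and 69% without.
- At correlation 0.8, where patients attend nearly all or nearly none, the gain falls to about 7-9 points.
- A proportional-odds model, in four settings of 400 replicates, gave 61% versus 88%, 45% versus 70%, 41% versus 59% and 71% versus 90%: gains of 27, 25, 18 and 19 points, each with simulation error of up to about 3 points.
- With 12 correlated predictors in the model (pairwise correlation 0.2), closer to the planned regression, logistic power was 39-64%. An overdispersed binomial model on the count had 46-81%. The gain was 7-20 points across nine settings.
- Rejection under the null was about 4-7% for the cut and the count analyses.

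**Step 3: wider count patterns.** With effects set so that the rank test has about 80% power, the loss ran from about 5 points (skewed negative binomial counts, mean 2, 21% reaching 4) to about 43 (mean 8, 73% reaching 4, compared with a linear model on the count).

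**Step 4: two classes.** Suppose engagers attend about 80% of sessions and non-engagers about 10%, and the predictor acts on class membership. Logistic regression at 4 or more then beats the rank test by about 7-18 points, for example 62% versus 52%. Here the cut separates the two classes almost perfectly, and the variation within each class is noise.

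**The case against.** The strongest reply is that the yes/no outcome is deliberate and useful. It matches the adherence definition in the CACE analysis, and its fitted probabilities supply the propensity subgroups. Whether a patient reached a predefined amount of support is a fair question. This stands: the logistic model should not be removed.

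Second, no single power loss can be read off the plan. This also stands. A reader might infer that the cut costs a fixed amount, such as 13-25 points. The documents do not support that, because the result depends on an attendance pattern, an effect size and a reference power that they do not give. Under the two-class pattern in step 4 even the direction changes.

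Third, the analysis is exploratory, within one arm, with no stated hypothesis and no claimed power. A reader might infer that the efficacy results are weakened. They are not: no primary or secondary efficacy comparison uses these regressions, and the CACE estimate needs only the definition of adherence.

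Fourth, a count is not automatically a better measure of engagement. The protocol's Peer support program intervention section has the matched mentor telephone people who miss an event, so more calls may reflect less attendance. This stands as a caution for the phone count. It is also a reason not to rely on one combined count of all encounters.

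What remains is that the plan contains no analysis of the counts at all, although its stated aim concerns attendance and contacts.

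**Conclusion.** The point holds as a cheap improvement. All three participation outcomes are cut at 4, and nothing in the section uses the underlying counts. With smooth variation in attendance, 8 sessions, about 145 patients and roughly 30-70% reaching 4, the cost is about 7-25 points of power for a given predictor. The low end comes from the 12-predictor model and from highly clustered attendance; the high end comes from proportional-odds models and the normal-theory figure at a 30% share. One small simulation setting reached 27. Outside those conditions the loss ranged from about 5 to 43 points, and under a clear engager/non-engager split the cut performs better. The documents do not say which pattern to expect, which is itself a reason to plan both analyses.

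**What to change.** In the SAP's Intervention Implementation Analysis, add two models with the same baseline predictors:

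- for group support, an overdispersed binomial or proportional-odds model for the number of sessions attended out of 8, counting a get-together or its catch-up call;
- for 1:1 support, a negative binomial model for the number of phone encounters.

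Keep the logistic model at 4 or more for the CACE-aligned definition and for the propensity-for-adherence subgroups in the Heterogeneity of Treatment Effect section. State that phone counts are to be read alongside attendance, since missed events prompt calls.

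The cost is a few lines of SAP text and a little more analysis. No new data should be needed: applying rules of at least 2 and at least 4 encounters already requires a count per patient, although the documents do not describe an attendance log and this should be confirmed.

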together, participated in a BREATHE call, or by having a phone conversation with their BREATHE pal containing discussion of COPD-related issues (determination based on BREATHE pal notes.) For a more detailed description of our complier-average causal effect analysis and IV approach, please refer to the statistical analysis plan in the supplemental study documents section (SAP_BREATHE2_2019Jun26).

The sample size calculation will be based on an overall comparison of the change between the baseline and 6-month measurements of the patients on the St. George scale (primary outcome) in the two arms (interaction term). The unadjusted per-arm sample size is based on a power of 0.80, alpha of 0.05, a minimally clinical significant difference in change scores of 4 points and a meta-analysis estimate of variability. The estimated sample size is 145 patients per arm, after accounting for a 15% attrition rate, assuming a within-patient correlation between measurements of 0.8.

Heterogeneity of Treatment Effects (HTE) HT-1

The goal of the HTE analyses in this study is to consider the difference in treatment effect between the two arms, taking into consideration differences in the arms that are not obviously accounted for in the balance created by the randomization scheme. Patient characteristics such as disease severity or caregivers' presence may show differences in the intervention's effect and thus are important avenues to explore for hypothesis generation. In this hypothesis generating HTE analysis, we will consider the following subgrouping variables: age (4 categories), gender, disease severity, baseline PAM score, and caregiver presence. Within the HCP PLUS Peer Support group, we will also consider subgrouping by the propensity for adherence to treatment.

HT-2, HT-3

Subgroup treatment effects will be estimated by including a three-way interaction between the subgroup variable, the study assignment variable, and the 6-month time variable in a generalized linear mixed RE model. We will test for a difference in treatment effect between subgroups by a hypothesis test of the overall three-way interaction in this model. We will report estimates of subgroup treatment effects with corresponding 95% confidence intervals (CIs). For a more detailed description of the heterogeneity of treatment effect, please refer to the statistical analysis plan in the supplemental study documents section (SAP_BREATHE2_2019Jun26).

- d. Early stopping rules.
No early stopping rules.

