The study will compare the impact of these strategies on the outcomes of health-related quality of life, mortality, and use of Emergency Department (ED) and other hospital services, as well as intermediate measures such as patient activation, self- efficacy, and self-care behavior, as described in the BREATHE2 Study Conceptual Model shown in Figure 1 below. At the same time, the study will compare the impact of these strategies on caregiver self-efficacy, stress, and coping skills. We will also assess both patient and caregiver experience and satisfaction within the HCP PLUS Peer Support Group.

[figure not shown]

Figure 1. BREATHE2 Study Conceptual Model

Study Design (PCORI Standard IR-1)

Phase 1 of this study involved intervention development followed by peer mentor recruitment and training. Phase 2 of this study, which is addressed by this SAP, involves rigorous testing of the study intervention in a randomized controlled trial (RCT) at two study sites: (1) Johns Hopkins Bayview Medical Center (JHBMC) and affiliated pulmonary and primary care clinics and (2) Howard County General Hospital (HCGH) and affiliated pulmonary and primary care clinics. (some of these clinics are part of Johns Hopkins Community Physicians). Thus within each study site, patients were recruited from two clinical settings: (1) inpatient recruitment within the hospital and (2) outpatient recruitment from the affiliated clinics.

We consented and enrolled 290 persons who met the initial eligibility criteria of receiving a physician diagnosis of COPD and treatment for it. Patient participants were randomized to one of the two study groups in this trial (HCP or HCP PLUS Peer Support) and their respective Caregiver Participant, if they have one enrolled, participated with them in that study group. Then patients were randomized 1:1 to the HCP or the HCP PLUS Peer Support.

Our primary study outcome is the change in quality of life (QOL) over the 6 months post discharge. Other patient measures include patient activation self-efficacy, self-care behavior,

health status, used of Emergency Department (ED) and other hospital services, and survival. Caregiver measures include caregiver self-efficacy, stress, and coping skills.

Intervention Description

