gender, disease severity (whether they are on continuous home oxygen), baseline PAM score (collapsed into low vs high levels), and caregiver presence (caregiver vs no caregiver). Within the HCP PLUS Peer Support group, we will also consider subgrouping by the propensity for adherence to treatment (collapsed into low vs high levels), with propensity for adherence to treatment as the estimated probability of adherence to treatment from our intervention implementation analysis described above.

HT-2, HT-3:

Subgroup treatment effects will be estimated by including a three-way interaction between the subgroup variable, the study assignment variable, and the 6-month time variable in a generalized linear mixed RE model. We will test for a difference in treatment effect between subgroups by a hypothesis test of the overall three-way interaction in this model. We will report estimates of subgroup treatment effects with corresponding 95% confidence intervals (CIs). For the comparison of propensity for adherence groups within the HCP PLUS Peer Support group, we will include an interaction between the subgroup variable and the 6-month time variable, test this interaction, and estimate subgroup effects with corresponding 95% CIs.

References

1. Jones PW. St George's Respiratory Questionnaire Manual. 2009;44(June):0-16.
3. PROMIS. Anxiety. A brief guide to the PROMIS Anxiety instruments. 2018:1-18.
4. PROMIS. Depression. A brief guide to the PROMIS Depression instruments. 2018:1-18.
5. PROMIS. Emotional Support. A brief guide to the PROMIS Emotional Support instruments. 2017:1-6.
6. PROMIS. Instrumental Support. A brief guide to the PROMIS Instrumental Support instruments. 2017:1-6.
7. PROMIS. Social Isolation. A brief guide to the PROMIS Social Isolation instruments.

2015:1-7.

8. PROMIS. Informational Support. A brief guide to the PROMIS Informational Support v2.0 instruments. 2015:1-7.

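### The low/high propensity subgroup uses in-sample probabilities from an over-fitted participation model, so actual participation leaks into a split meant to reflect baseline characteristics; cross-fitting removes the leak

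*Combined protocol and SAP*

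**What the plan says.** The SAP section Intervention Implementation Analysis states: "We will use multivariable logistic regression to predict overall participation, as well as participation in group or 1:1 support". Each outcome is yes/no, with participation meaning four or more encounters of the relevant kind. These outcomes exist only in the HCP PLUS Peer Support arm. The predictors are given as examples, so the list is open: age, gender, education, distance, oxygen use, living alone, having a caregiver, self-rated health, PAM level, and baseline hope, support, anxiety and depression scores.

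The SAP section Heterogeneity of Treatment Effect then adds a subgroup comparison within that arm. It defines "propensity for adherence to treatment as the estimated probability of adherence to treatment from our intervention implementation analysis", collapses this into low and high, tests its interaction with the 6-month time variable for SGRQ, and reports 95% confidence intervals. Protocol section 7c mentions the same subgrouping.

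Neither document states a selection rule, penalty, cross-validation, optimism correction or cut-point for low versus high. The HTE analyses are labelled hypothesis generating.

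**The concern.** A logistic model with many terms and few participants per term fits chance features of the sample. Its fitted probabilities are then pulled towards what each patient actually did. Splitting those same patients on these probabilities produces a grouping that is called baseline propensity but partly encodes participation observed after randomisation.

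This matters because participation can be tied to outcome for reasons unrelated to propensity. Patients who are doing well may attend more. Under the SAP's missing-data rule a patient who dies is scored 100 on the SGRQ, and an early death also leaves less time to reach four encounters. Any such link enters the high-low comparison of SGRQ change and can be read as evidence that a type of patient, identifiable at baseline, fares better with peer support.

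**Working it through.** **Arm size.** SAP, Study Design: "We consented and enrolled 290 persons who met the initial eligibility criteria" and "Then patients were randomized 1:1 to the HCP or the HCP PLUS Peer Support". So 290 / 2 = 145 patients.

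**The plan's own figure.** Protocol section 7c: "The estimated sample size is 145 patients per arm, after accounting for a 15% attrition rate". Its inputs are "a power of 0.80, alpha of 0.05, a minimally clinical significant difference in change scores of 4 points", "a meta-analysis estimate of variability" (no number given) and "assuming a within-patient correlation between measurements of 0.8". Without an SD the 145 can only be back-solved, here taking alpha as two-sided:
- SD of change = SD × √(2 × (1 − 0.8)). With SD 17.7 this is 11.2.
- n = 2 × (1.96 + 0.84)² × 11.2² / 4² ≈ 123, and 123 / 0.85 ≈ 145.
- SD 17 gives 135 and SD 18 gives 151. The 11.2 is used below as an assumption.

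**Number of terms.** Nine single characteristics + hope (1) + six PROMIS scores (those named under the SAP's intermediate measures) = 16 at one term each, or 15 if social isolation is not counted as support. Categorical coding adds terms: oxygen use has three levels in the protocol's outcome table.

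**Participants per term**, using whichever of participants and non-participants is fewer, with 16 terms. Uptake is assumed:
- 20%: 145 × 0.2 / 16 = 1.8
- 30% or 70%: 145 × 0.3 / 16 = 2.7
- 50%: 145 × 0.5 / 16 = 4.5

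With the 325 patients planned in the protocol summary (162 per arm), the best case is 162 × 0.5 / 16 = 5.1.

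**Simulation.** 145 patients; 16 predictors with pairwise correlation 0.2; none or four truly predictive; unpenalised logistic regression; median split of the fitted probability; 1,500 datasets per row. The excess gap is the observed high-low gap in participation minus the gap in true probabilities.

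| Uptake | True AUC | Apparent AUC | AUC in new patients | Observed participation, high / low | True probability, high / low | Excess gap (points) |
|---|---|---|---|---|---|---|
| 30% | 0.50 | 0.70 | 0.50 | 42 / 18% | 30 / 30% | 24 |
| 30% | 0.65 | 0.75 | 0.58 | 45 / 15% | 35 / 25% | 20 |
| 30% | 0.70 | 0.78 | 0.64 | 47 / 13% | 39 / 21% | 16 |
| 30% | 0.75 | 0.81 | 0.70 | 49 / 11% | 42 / 18% | 14 |
| 50% | 0.50 | 0.69 | 0.50 | 64 / 37% | 50 / 50% | 27 |
| 50% | 0.65 | 0.74 | 0.59 | 67 / 33% | 57 / 43% | 20 |
| 50% | 0.70 | 0.77 | 0.65 | 70 / 30% | 60 / 39% | 19 |
| 50% | 0.75 | 0.81 | 0.71 | 73 / 27% | 65 / 35% | 16 |

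The leak is largest with no signal but does not vanish when the predictors are real.

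**Carry-over to SGRQ.** False difference ≈ excess gap × the assumed extra improvement in adherers.
- No signal, 4 points: 0.24 to 0.27 × 4 = 0.96 to 1.08
- No signal, 8 points: 0.24 to 0.27 × 8 = 1.92 to 2.16
- With signal (gap 0.14 to 0.20): 0.56 to 0.80 at 4 points, 1.12 to 1.60 at 8 points

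**False-positive rate, no signal.** The SE of the difference in mean change between halves is about 11.2 × √(4/145) = 1.86. The rejection rate is P(|Z + d/SE| > 1.96).
- d = 0.96 to 1.08: d/SE = 0.52 to 0.58, rate 8 to 9%
- d = 1.92 to 2.16: d/SE = 1.03 to 1.16, rate 18 to 21%

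Direct simulation gave 8 to 9% at 4 points and 17 to 19% at 8 points.

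**Same data, 10-fold cross-fitted probabilities.** The high-low difference was at most 0.24 points in absolute value, with rejection of 5 to 6%.

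**The case against.** The strongest reply is that this is a minor part of the plan. The propensity split is something the SAP will merely consider, within analyses labelled hypothesis generating. The primary ITT test does not use the model, and the CACE uses randomisation as its instrument. The predictor list is open, so 16 terms in one model is not a commitment. All of this stands and limits the weight of the point. The implementation section itself, however, carries no hypothesis-generating label.

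A reader might infer that the named predictors and the high-propensity patients will be largely noise. The documents do not support that: it requires predictors with almost no signal, and they give neither uptake nor predictor strength. With 16 terms and a true AUC of 0.65 to 0.75, about 71 to 81% of patients still fall in the correct half.

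A reader might also infer that odds ratios will be inflated about threefold, from calibration slopes of 0.31 to 0.34 in a simulation with four real predictors of log OR 0.3. That slope describes the summed linear predictor in new patients. In that setting the mean single coefficient was 0.35 against a true 0.30, an excess of about one sixth, and the false-positive rate per null predictor was about 6%. Low power and ordinary multiplicity are the larger problems for individual predictors.

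It is also fair to say that compulsory ridge or lasso would give up the per-predictor inference that the section's aim, finding characteristics related to participation, relies on. Finally, the propensity comparison lies within one arm and has no control contrast. Cross-fitting does not change that.

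**Conclusion.** The point holds for the construction of the propensity subgroup. Fitted probabilities from a model with at most about 4.5 participants per term (16 terms, 145 patients) are reused in the same patients, so the low/high split leaks actual participation. Under the no-signal assumption the leak is 24 to 27 percentage points at 30 to 50% uptake. The resulting false SGRQ difference is about 1 to 2 points if adherers improve 4 to 8 points more, against a stated minimum important difference of 4. The false-positive rate rises above 5%, to roughly 17 to 21% at the 8-point assumption. With real predictors the leak is smaller, 14 to 20 points in the settings run.

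These sizes rest on assumptions the documents cannot settle: uptake, predictor strength and correlation, a median split, the adherer advantage, and an SD of change of 11.2 back-solved from the sample size. The direction of the problem does not depend on them, provided participation and outcome are linked beyond what baseline predicts.

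The documents do not support extending the point to the primary ITT result or the CACE, or concluding that the participation models are worthless.

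**What to change.** In the SAP section Heterogeneity of Treatment Effect, define propensity for adherence as a cross-fitted probability: each patient's value comes from a model fitted without that patient, for example by 10-fold cross-fitting. State the low/high cut-point at the same time. In Intervention Implementation Analysis, report an optimism-corrected c-statistic for each of the three participation models.

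The cost is a few lines of code, no new data and a slightly noisier split. In simulation with four real predictors, leave-one-out probabilities placed 70 to 73% of patients in the correct half, against 72 to 74% in-sample.

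Penalised regression or a shorter pre-specified predictor list is optional. Either would reduce over-fitting, but penalisation gives up the usual p-values and confidence intervals for each predictor.
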